In Nigeria, approximately 3.2 million people were living with human immunodeficiency virus (1)/acquired immunodeficiency syndrome (AIDS) in Nigeria (2). Nigeria has about 196,000 adolescents (10-19 years) living with HIV with an estimated 17,000 new infections and 11,000 AIDS-related deaths per year in the age group (3). Adolescents aged 15 to 19 years constitute 8.8% of Nigeria's over 173 million people and have an HIV prevalence rate of 2.9% (3).

Non-adherence to antiretroviral therapy (ART) increases the risk of non-suppression of HIV, secondary HIV transmission, and development of drug resistance; it has a negative impact on treatment outcomes, leads to decreased survival and worsened quality of life (4, 5). Adolescents on ART have lower viral suppression rates (49%) when compared with both adults and younger children (72.8% and 57%) and this is frequently a consequence of lower adherence to ART (6, 7).

The non-maintained ART adherence is a major barrier to the achievement of optimal treatment outcomes among adolescents living with HIV. ART adherence is a challenge among adolescents living with HIV because of lack of appropriate information, their unique emotional state and lifestyles. Religious, cultural, social and health services related factors have also been recognized as a source of non-adherence to ART treatment (8). Other known barriers to ART adherence include difficult dosing schedule, side effects, food restrictions and pill burden but the most commonly quoted challenge to adherence is forgetting to take antiretroviral drugs (9-11). Many strategies, including directly observed drug use, adherence counseling, telephone calls and reminder devices adopted to enhance ART adherence have turned out to be time-consuming, costly and intrusive (4, 11, 12).

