The National Agency for the Control of AIDS (NACA) is the government agency that facilitates the engagement of all tiers of government and all sectors on issues of HIV/AIDS prevention, care, and support in Nigeria. Each of the 36 states in Nigeria has an agency for the control of AIDS that performs similar functions at the state level. The Ogun State Agency for the control of AIDS (Ogun SACA) which was established as an agency by an act of the Nigerian Parliament in 2009 is responsible for the coordination of all the organizations and efforts for the control of HIV and AIDS in Ogun State, Nigeria. The Ogun State and other state agency for AIDS control oversee the implementation of national and sub-national policies and directives on HIV/AIDS in collaboration with various donor agencies and implementing partners. They work with local and international development partners and health facilities to provide antiretroviral drugs for PLHIV including adolescents. They also, through their affiliated health institutions also provide adherence support for the PLHIV.

PROJECT GOALS

The aim of this study is to evaluate the feasibility, acceptability, and efficacy of interactive and tailored SMS reminders on ART adherence among adolescents (15-19 years) living with HIV in Southwest, Nigeria. The feasibility of using personal mobile phones and retaining participants throughout the study period will be assessed. The study will be carried out among adolescents living with HIV who have less than optimal level of adherence to ART (<95%) since they are most likely to benefit from the SMS reminders. The study will create an occasion to educate adolescents living with HIV/AIDS on self-care.

PROJECT OBJECTIVES

Objective 1: To evaluate the effect of interactive and tailored SMS reminders on ART adherence among adolescents (15-19 years) living with HIV in Southwest, Nigeria.

Objective 2: To assess the feasibility and acceptability of using personal mobile phones and interactive and tailored SMS reminders for the improvement of ART adherence among adolescents living with HIV in Southwest, Nigeria.

Objective 3: To identify the predictors of ART non-adherence among adolescents (15-19 years) living with HIV in Southwest, Nigeria.

STUDY HYPOTHESES

- a. Interactive and tailored SMS reminders are efficacious in the improvement of ART adherence among adolescents (15-19) years living with HIV.

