- b. The use of personal mobile phones for the improvement of ART adherence among adolescents living with HIV is feasible and acceptable.
- c. ART adherence among adolescents is predicted by demographic, socioeconomic, and psychosocial factors.

METHODOLOGY

The proposed study is targeted at adolescents living with HIV/AIDS who are on ART but are not adherent to medications. Two hundred participants will be recruited to participate in a randomized controlled trial to evaluate the effectiveness of interactively tailored SMS reminders on the improvement of ART adherence. The study will be conducted in Ogun State in the southwestern part of Nigeria over a 52-week period.

Participants and setting

Nigeria has 36 states in six geo-political zones. The Southwest geopolitical zone is one of the six and consist of six states namely, Ogun, Lagos, Oyo, Osun, Ondo and Ekiti states. The study will be based in Ogun State and extend to the other five states in Southwest Nigeria in order to meet recruitment goals. Ogun State is one of the 36 states in Nigeria. Ogun State has an estimated 161,200 PLHIV living with HIV and an HIV prevalence rate of 3.1%. Thirteen thousand five hundred (13,500) PLHIV are currently accessing antiretroviral drugs across 24 treatment clinics in the State.

Study design and procedure

A single-blind, parallel-design (ratio 1:1), and multi-center RCT of 200 adolescent living with HIV who are non-adherent to medications will be conducted over a one-year period at HIV clinics in Ogun State and other states in Southwest Nigeria. This study is designed to have 80% power to detect a difference of 20%. When the proportion of adolescents who are adherent to ART was taken as 49% (6) and 10% attrition rate, a sample size of 96 per group was obtained using STATA 15/C statistical software. The study will recruit 200 participants from the ART clinics in Southwest Nigeria into a randomized controlled trial (RCT). Convenience sampling method by which participants will be recruited on routine clinic visits across five (5) high patient-density ART sites will be used.

Participants' recruitment

Recruitment of participants will occur over a three-month period. Recruitment will be based on five eligibility criteria namely:

- a. HIV seropositivity
- b. Being on ART for at least six months
- c. Age 15 to 19 years as at last birthday
- d. Use of personal mobile phone
- e. Poor adherence to ART

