For the purpose of this study, we defined poor adherence as self-reported < 95% adherence in the preceding one month using a validated visual analogue scale (25, 26). Self-reported 95% adherence level is an ideal cut-off point because self-reported measures tend to exaggerate adherence and such high adherence level will minimize the occurrence of false-negatives (27). Adolescents who are too ill to require hospital admission will be excluded from the study.

Initial eligibility screening and recruitment will be carried out by the primary caregivers using a checklist. Potential participants who meet the first four criteria will be presented with a visual analogue scale (VAS) labelled 0 to 100% at intervals of 5%. They will be educated on the implication of various percentages e.g. 0%, 50%, and 100%. They will be required to put a mark on the line at the point that shows their best guess about how much of their prescribed ART medication they had taken in the preceding one month (4 weeks). Volunteers who choose points less than 95% mark will be regarded as being non-adherent to ART and will be eligible to participate in the study. Eligible and willing participants will then be referred to the research assistants for a comprehensive informed consent process.

Baseline activities

At the baseline, the research assistants will give the volunteer participants a detailed explanation of the study, including its aim, duration, intervention and possible benefits. All the volunteers will be required to give a signed informed consent in a private room. Adolescents aged 15 to 19 years are thought to be relatively mature. According to a brief of AIDS regulations and Laws in Nigeria, children who are deemed mature in this context are capable of giving informed consent (28). Besides, based on evidence from South Africa and Lesotho, the WHO recommended that the legal age of consent for HIV testing and treatment should be 12 years (29). The consenting volunteers will then be allocated unique identifiers that they will maintain throughout the course of the study. The contact details of the lead investigator will be made available to the participants so that he can be reached directly for any reason that is related to the study. Baseline data will be obtained in a private room by trained research assistants using structured interviewer-administered paper-based questionnaires over a period of about 40 minutes. The questionnaire will assess:

1. Socio-demographic variables.

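### The 96 per group does not contain its stated 10% attrition under a two-sided 5% test (200 randomised gives about 78% power), and the 49% behind it is given elsewhere as viral suppression

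*Combined protocol and SAP*

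**What the plan says.** The sample size is in the Study design and procedure section.

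- Power and effect: "This study is designed to have 80% power to detect a difference of 20" per cent.
- Reference proportion, citing reference 6: "When the proportion of adolescents who are adherent to ART was taken as 49% (6").
- Attrition and result: "10% attrition rate, a sample size of 96 per group was obtained using STATA 15/C statistical software".
- Planned size: "The study will recruit 200 participants from the ART clinics in Southwest Nigeria", allocated 1:1.

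Neither this section nor Data Analysis or Statistical Methods gives an alpha, a sidedness, the test being powered, or whether the 20% is absolute or relative.

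The Background uses the same percentage for another quantity, citing references 6 and 7: "Adolescents on ART have lower viral suppression rates (49%) when compared with both adults and younger children". It adds that "this is frequently a consequence of lower adherence to ART (6, 7").

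On eligibility, the Participants' recruitment section says: "Volunteers who choose points less than 95% mark will be regarded as being non-adherent to ART". Only these volunteers may enter.

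Statistical Methods compares the proportion at or above 95% at the end of follow-up with baseline, by chi-square. The between-arm test it names is an independent t-test on mean adherence. It also lists relative risk, risk difference and odds ratio as effect measures.

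**The concern.** A two-proportion sample size can be reproduced only if alpha, sidedness, scale and test are known, and all four are missing. On the usual assumptions the stated 96 sits next to the requirement before attrition, although the text says attrition was an input. If attrition was left out, neither 96 per group nor the planned 200 delivers the 80% claimed.

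The 49% is a second, independent problem. It is called the adherent proportion in the calculation and viral suppression in the Background, which treats low suppression as often resulting from low adherence. The document therefore regards them as different quantities. By the trial's own cut-off, no participant is adherent at entry. The 49% can then only be an assumed control-arm proportion at follow-up, and the protocol neither says this nor supports it.

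**Working it through.** **Inputs from the protocol:** power 80%, difference 20%, reference 49%, attrition 10%, ratio 1:1, 96 per group, 200 in total.

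**Assumed, not stated:** alpha 5%; absolute difference, so 49% vs 69%; arms compared on proportions.

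**Scale.** A relative 20% (49% to 58.8%) needs 405 per group two-sided or 319 one-sided, before attrition. Only the absolute reading is near 96.

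**Requirement, two-sided 5%, pooled variance.** With p̄ = 0.59:

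n = [z_α √(2p̄(1−p̄)) + z_β √(p₁q₁ + p₂q₂)]² / δ²

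= [1.960 × √(2 × 0.59 × 0.41) + 0.8416 × √(0.49 × 0.51 + 0.69 × 0.31)]² / 0.2²

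= [1.3633 + 0.5732]² / 0.04 = 93.7, so 94.

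With 10% attrition: 94 / 0.9 = 104.4, so 105 per group (210 in total).

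**Trying to reproduce 96 (49% vs 69%, 80% power):**

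| Reading | Before attrition | After 10% attrition |
|---|---|---|
| Two-sided 5%, pooled | 94 | 105 |
| Two-sided 5%, unpooled | 92 | 103 |
| Two-sided 5%, continuity-corrected | 104 | 116 |
| One-sided 5%, pooled | 74 | 83 |
| One-sided 5%, continuity-corrected | 84 | 94 |

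No reading gives exactly 96, and two come within 2 of it: two-sided pooled without attrition (94), and one-sided continuity-corrected with attrition (94). No two-sided 5% reading that includes attrition needs fewer than 103.

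**Power at the sizes in the protocol, two-sided 5%.** Power = Φ{[δ√n − z_α √(2p̄(1−p̄))] / √(p₁q₁ + p₂q₂)}.

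- 200 less 10%, so 90 per arm: (1.8974 − 1.3633) / 0.6810 = 0.784, and Φ = 78.4%. Exact enumeration of the Pearson test gives 78.8%; the unpooled formula gives 79.6%.
- 96 less 10% = 86.4, so 86 per arm: (1.8547 − 1.3633) / 0.6810 = 0.722, and Φ = 76.5% (unpooled 77.7%).
- 96 per arm with no loss: 80.9%.

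The shortfall at the planned size is therefore 0.4 to 1.6 points. At 90 per arm, 80% power corresponds to a difference of 20.4 points (pooled).

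**Power if the test was one-sided 5% with continuity correction.** Replace δ by δ − 1/n and use z_α = 1.645, so that z_α √(2p̄(1−p̄)) = 1.1441.

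- 86 per arm: (1.7469 − 1.1441) / 0.6810 = 0.885, and Φ = 81.2%.
- 90 per arm: (1.7920 − 1.1441) / 0.6810 = 0.951, and Φ = 82.9%.

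The uncorrected one-sided values are higher (85% and 87%), but they belong to a method that needs only 83 after attrition and so does not explain 96.

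**Sensitivity to the 49%.** At 90 per arm, two-sided 5%, +20 points, pooled:

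| Control rate | 10% | 20% | 30% | 40% | 49% | 60% |
|---|---|---|---|---|---|---|
| Power | 92% | 84% | 79% | 77% | 78% | 84% |

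Power is below 80% only for control rates of about 27% to 53%.

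**The case against.** **The text says attrition was included, and a one-sided design would bear that out.** One-sided 5% with continuity correction needs 94 after attrition, so 96 would be enough, and the efficacy hypothesis is directional: "Interactive and tailored SMS reminders are efficacious in the improvement of ART adherence among adolescents". This stands to the extent that 96 cannot be called an arithmetic error outright. A reader might infer such an error, but the documents do not support it while alpha and sidedness are unstated. A directional hypothesis does not establish a one-sided test, however, and none is named anywhere. Two-sided remains the natural reading.

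**The powered comparison is itself assumed.** Statistical Methods tests the proportion against baseline, and its named between-arm test is a t-test on means. This is correct, and every power figure here depends on the assumption. Because the calculation starts from a proportion, and risk difference and relative risk are listed effect measures, a between-arm comparison of proportions is the reasonable reading. The protocol should say so.

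**Viral load is one of the listed adherence measures, so 49% may be a deliberate proxy.** That is possible, but the protocol does not state the link, and suppression is not the same outcome as at least 95% adherence.

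**The effect is small.** It is. A reader might infer that the trial is seriously underpowered, or that a wrong 49% must lower power. Neither follows: the shortfall at 200 is under 2 points, and low control rates, plausible when all enter below 95%, raise power for the same 20 points.

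**Conclusion.** The point holds in conditional form. Under a two-sided 5% test of 49% vs 69% between arms, without continuity correction, 96 per group omits the attrition it claims to include: 94 are needed before and 105 after. The planned 200 gives about 78% power instead of 80%. If the test was one-sided 5%, there is no shortfall, but the protocol does not say that it was.

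Two parts need no assumption about alpha. The inputs required to reproduce the claim are missing, and 49% carries two labels with no support as the week-20 control proportion at or above 95%. These matter more than the small loss of power. The documents do not show that more patients are needed.

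**What to change.** In Study design and procedure:

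1. State two-sided 5%, that the 20% is an absolute difference, which between-arm test of proportions is powered, and the Stata inputs used. Align Statistical Methods so that it names that between-arm test.
2. Replace the claim with: *94 evaluable per group (105 with 10% attrition) give 80% power for 49% vs 69%; with 200 randomised and 10% attrition, power is about 78%.*
3. If a one-sided 5% continuity-corrected test was in fact used, say so, keep 96, and report the matching power: about 81% at 86 evaluable per group and 83% at 90.
4. State what the 49% represents and why it applies to the control arm at week 20, or replace it with a justified assumption. Relabelling it without a reason would not be enough. Acknowledge that the Background gives the same figure as viral suppression.
5. Show power over a range of control rates. At 90 per arm, two-sided 5%, +20 points: about 92% at 10%, 84% at 20%, 77% at 40% and 84% at 60%.

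Cost: text only, with no added patients. The downside is a slightly less favourable stated power, about 78% instead of 80%, if the test is two-sided.

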HIV viral load estimation will be done in line with APIN Public Health initiative program and in accordance with the national guideline. Sample collection, handling and disposal follows the standards and guidelines outlined by the WHO and PEPFAR (36, 37). The participants' capability to operate mobile phones will be enhanced. The research assistants will work with participants to select from a list the most preferred SMS that will serve as a daily reminder of ART adherence. Each participant will select an SMS format that will serve as a reminder for follow-up visit reminders. In addition, the participants will also choose the preferred language and time for SMS reminders. The participants will receive the adherence counseling by trained counselors. The messages will be designed in such a way that they are sensitive and protect the privacy of the participants. The participants will be able to contact the lead investigator if they wish to change their chosen messages or if the services to their mobile phones are disrupted.

Randomization

The Project will collaborate with an accredited medical internet technology solutions firm (Golden Business Resource Limited) to set up a database system for dissemination and receipt of SMS. Following baseline

activities, the participants will be randomly allocated to intervention and control groups by the database administrator. Random allocation will be achieved through a computer-generated simple randomization scheme. The investigators, data manager, research assistants, counselors and other project staff will be blinded throughout the study.

Intervention

All the participants will receive one SMS reminder each for follow-up appointments 48 hours and 24 hours before the follow-up visit date. The participants that are allocated to the intervention group will also receive daily ART adherence reminder SMS. Participants in the intervention group will be required to send reply SMS to their daily messages as soon as possible. They will be expected to send '1' if they find the reminder acceptable depending on the circumstance around them at the time the message is received. They will be expected to send '2' if it was not so acceptable.

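### Allocation is not stratified by ART site and the analysis does not name site: a cheap improvement in within-site balance and precision is available, with little power at stake

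*Combined protocol and SAP*

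**What the plan says.** Study design and procedure describes "A single-blind, parallel-design (ratio 1:1), and multi-center RCT of 200 adolescent living with HIV who are non-adherent to medications" and recruitment "across five (5) high patient-density ART sites will be used". The same section gives the planning basis: "This study is designed to have 80% power to detect a difference of 20" percent, with "the proportion of adolescents who are adherent to ART was taken as 49% (6) and 10% attrition rate", from which "a sample size of 96 per group was obtained".

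The Randomization section places allocation after the baseline activities, in the hands of the database administrator at an outside firm. The method is: "Random allocation will be achieved through a computer-generated simple randomization scheme". Blocks, strata and minimisation are not mentioned anywhere.

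Under Statistical Methods, the named tests are a chi-square test of the proportion adherent at the end of follow-up against baseline, and an independent t-test of mean adherence between groups after each visit. Neither adjusts for site. Multiple regression is planned for possible confounders, but no covariate is named.

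**The concern.** The clinic may well be prognostic for adherence. The Background lists factors related to health services among the causes of non-adherence, and the section on secondary outcomes treats satisfaction with care as a strong predictor of it. Under unrestricted allocation, each clinic's participants divide between the arms by chance. If clinics differ in adherence, an unadjusted comparison carries that site-mix difference as extra noise.

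At stake are some precision and the face validity of the comparison in a multi-centre trial. The protocol deals with site neither in the allocation nor by name in the analysis.

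**Working it through.** **Inputs.** From Study design and procedure: N = 200, 1:1, five sites, 49% adherent, a 20-point difference, 80% power, 10% attrition, 96 per group. Assumed, because the documents do not give them: independent 1:1 assignments, 5% significance level, a direction of 49% to 69%, 40 participants per site, and the range of site adherence rates.

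**1. The plan's 96 per group.** Normal approximation for two proportions, with mean p̄ = 0.59:

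n = [1.96·√(2·0.59·0.41) + 0.842·√(0.49·0.51 + 0.69·0.31)]² / 0.20² = 93.7, so 94.

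With attrition, 94/0.9 = 104.4, so 105. A one-sided test with continuity correction gives 84, then 84/0.9 = 93.3, so 94. Neither the significance level nor sidedness is stated. No variant tried gives exactly 96, though the one-sided corrected version comes within 2.

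**2. Overall arm sizes.** With Binomial(200, 0.5), both arms reach 96 only if the intervention arm has 96 to 104 participants. That has probability 0.475, so at least one arm falls below 96 with probability 0.525.

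**3. What an uneven split costs.** Power = Φ{[0.20 − 1.96·√(0.59·0.41·(1/n₁+1/n₂))] / √(0.49·0.51/n₁ + 0.69·0.31/n₂)}, with 90% of each arm retained.

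| Randomised | Power |
|---|---|
| 96:96 (the planned minimum) | 76.7% |
| 100:100 | 78.4% |
| 95:105 | 78.2–78.3% |
| 90:110 | 77.8–78.1% |
| 86:114 | 77.4–77.8% |
| Average over simple randomisation of 200 | 78.2% |

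Ranges depend on which arm is larger. The average loss against 100:100 is about 0.2 points. A draw of 200 has less power than 96:96 in about 0.5% of cases.

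**4. Balance within sites.** With Binomial(40, 0.5), a split of 25:15 or worse has probability 0.154 at a given site. For at least one of five sites, 1 − (1 − 0.154)⁵ = 0.57. The chance that the smaller arm holds under 40% of a site is 26% for a site of 20, 20% for 30, 15% for 40 and 9% for 60.

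**5. Site-mix difference between arms.** With five equal sites and evenly spaced rates, the standard deviation (SD) of the difference in expected adherence is about 2·SD(site rates)/√200.

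- Rates 29, 39, 49, 59, 69%: SD(site rates) = √[(400+100+0+100+400)/5] = 14.1 points, so 2·14.1/14.1 = 2.0 points. Simulation puts 3 points or more in about 15% of trials.
- Rates 39 to 59%: half of that, 1.0 point. Simulation gives about 0.3%.
- Rates 44 to 54%: essentially none.

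For scale, the ordinary standard error of the difference is √(2·0.49·0.51/100) = 7.1 points.

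**6. What adjustment for site recovers.** A site split a:b carries 4ab/(a+b)² of the information of an even split. At 15:25 this is 4·15·25/1600 = 94%. The average for a site of 40 is 1 − 1/40 = 97.5%.

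**The case against.** The strongest reply is that simple randomisation of 200 participants is an accepted and valid method. That stands. Chance imbalance by site is not bias, and an unadjusted test already reflects it in its standard error. Even with site rates of 29% to 69%, simulated type I error is 5.2%. Adjusting for site also removes the site-mix difference, at a small cost in precision (step 6), and the protocol already foresees regression for confounders.

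A reader might infer from the 52.5% in step 2 that the trial loses its planned power more often than not. The documents do not support that. The plan recruits 200, not 192, and a 95:105 split, though short of 96 in one arm, has more power than 96:96.

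The 52.5% is itself conditional. The Timeline puts recruitment in weeks 9–21 and randomisation in weeks 22–25, so the firm could draw a fixed 100:100 list from a completed roster. The chance of falling below 96 would then be zero. The text does not say this is intended, and such a list would still leave sites unbalanced.

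Two further points have some force. Clinics may differ less than feared, because the trial supplies its own counselling: two counsellors, a single approach and a checklist for each session. And blocks are not wholly immune to guessing. The primary caregivers who screen and recruit are not named in the list of blinded staff, and participants know whether they receive daily messages.

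What remains is that site is left to chance in the design and is unnamed in the analysis, although both are easily remedied.

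**Conclusion.** The point holds as a modest, low-cost improvement in within-site balance and precision. It does not show that the trial is invalid or materially short of power because of its allocation method. The expected power cost is about 0.2 points, on the assumptions of 49% vs 69%, two-sided 5% and 10% attrition.

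A notable split in at least one site is more likely than not (57%) if sites enrol about 40 each. Its consequence depends on how far adherence differs between sites, which the documents do not report: a shift of 3 points or more is rare (about 0.3%) over a 39–59% range and not rare (about 15%) over a 29–69% range. These figures assume independent assignment, five equal sites and evenly spaced rates.

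That even 100:100 gives about 78% power under a two-sided 5% test is a separate matter of the sample-size calculation and is not caused by simple randomisation.

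**What to change.** In the Randomization section, replace the simple scheme with a computer-generated 1:1 list in permuted blocks of varying size, stratified by ART site, generated and held by the database firm. State that the list and block sizes are concealed from everyone who screens, recruits or assesses participants, including the primary caregivers.

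In Statistical Methods, name site as a covariate in the primary between-arm analysis.

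With blocks of 4, imbalance cannot exceed 2 at a site, or 5·2 = 10 overall, so the worst split of 200 is 95:105. With 40 at every site it is exactly 100:100. With varying sizes, the limit at each site is half the largest block.

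The cost is a different list from the same firm, a few sentences of text and slightly more analysis work. The added predictability is small, because allocation is central and follows baseline, and on the stated timeline recruitment ends before randomisation begins. No extra participants, visits or staff are needed.
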